4.2 Primary objectives

The primary goal is to compare and evaluate the physiological effects of terrestrial altitude and simulated altitude. For this purpose, the following parameters are measured:

Objective parameters:

- Perfusion of the skin microcirculation (flux)
- Blood oxygen saturation (%)
- Oxygen saturation of the muscles (%)
- Oxygen saturation of the brain (%)
- Heart rate (b/min)
- Blood pressure (mm/Hg)
- Skin temperature (°C)
- Lactate (mmol/l)
- Creatine kinase (U/L)
- Balance test (° & m/sec)

Subjective parameters:

- Pain sensation (N)

The primary goal is to compare and evaluate the psychological effects of terrestrial altitude and simulated altitude. For this purpose, the following parameters are measured:

Subjective parameters:

- Sleep Disorder Questionnaire
- Lake Louis Altitude Sickness Questionnaire
- Dyspnea questionnaire
- State of mind questionnaire
- Stanford Sleepiness Questionnaire
- Automated, cognitive test battery

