Skin temperature is measured via the iButton system (www.ibuttonlink.com). The self-adhesive sensors transmit the information about the skin temperature wirelessly to a computer. Furthermore, the skin temperature is recorded by means of a thermal imaging camera (FLIR). This measurement is measured during the baseline measurements, after the step-up task and up to 30 min after the cold water bath of the hand (5 min interval).

Lactate and creatine kinase

The lactate and creatine kinase measurement are carried out by capillary blood measurement (Accutrend, Roche Diagnostic, Rotkreuz, Switzerland & Reflotron, Roche Diagnostic, Rotkreuz, Switzerland). The affected area is disinfected and a superficial wound is pierced to take capillary blood. This measurement is measured during the baseline measurements, after the step-up task and up to 30 min after the cold water bath of the hand (5 min interval).

Balance measurement

The fluctuations of the hull are recorded and evaluated with the Sway Star™ System (www.b2i.info). The Sway Star™ is a measuring instrument that contains gyroscopes. It is attached to a belt that is placed around the patient's waist. The data is evaluated with the associated Sway Star™ software and transferred to the data sheet. This measurement is carried out after the baseline measurement and after the cold water bath immersion of the hand.

SUPSI

Figure: Measuring balance with the Sway Star™

Pain sensation

The pain threshold is measured using a pain pressure algometer (NOD, www.to-nod.com). As soon as the patient reports pain, this measurement is stopped. This measurement is carried out after the baseline measurement and after the cold water bath immersion of the hand.

Psychological measurements

The psychological measurements (sleep disorder, altitude sickness, dyspnea, state of mind, drowsiness) are evaluated on the basis of written questionnaires.

The cognitive test battery consists of 8 tasks (ANAM, US Department of Defence, Vista Life Sciences, USA), which are carried out on a laptop computer.

These measurements are carried out after the baseline measurement and after the cold water bath immersion of the hand.

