11 STATISTICAL METHODS

11.1 Hypotheses & Factors

Psychophysiological changes under simulated and terrestrial altitude.

Perfusion of skin microcirculation

- H0 The perfusion of the skin microcirculation does not change significantly at the simulated altitude compared to the terrestrial altitude.
- H1 The perfusion of the skin microcirculation changes significantly in the simulated altitude compared to the terrestrial altitude.

Oxygen saturation of the muscles and brain

- H0 The oxygen saturation of the muscles and the brain does not change significantly at the simulated altitude compared to the terrestrial altitude.
- H1 The oxygen saturation of the muscles and the brain changes significantly in the simulated altitude compared to the terrestrial altitude.

Oxygen saturation of the blood

- H0 The oxygen saturation of the blood does not change significantly in the simulated altitude compared to the terrestrial altitude.
- H1 The oxygen saturation of the blood changes significantly in the simulated altitude compared to the terrestrial altitude.

Blood pressure and heart rate

- H0 Blood pressure and heart rate do not change significantly at the simulated altitude compared to the terrestrial altitude.
- H1 Blood pressure and heart rate change significantly at the simulated altitude compared to the terrestrial altitude.

Skin temperature

- H0 The skin temperature does not change significantly at the simulated altitude compared to the terrestrial altitude.
- H1 The skin temperature changes significantly at the simulated altitude compared to the terrestrial altitude.

Lactate and creatine kinase

- H0 Lactate and creatine kinase do not change significantly at the simulated altitude compared to the terrestrial altitude.
- H1 Lactate and creatine kinase change significantly in the simulated altitude compared to the terrestrial altitude.

Equilibrium

- H0 The equilibrium does not change significantly at the simulated altitude compared to the

SUPSI

terrestrial altitude.

- H1 The equilibrium changes significantly in the simulated altitude compared to the terrestrial altitude.

Pain sensation

- H0 The sensation of pain does not change significantly in the simulated altitude compared to the terrestrial altitude.

- H1 The sensation of pain changes significantly in the simulated altitude compared to the terrestrial altitude.

Sleep disorder

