11.4.2 Primary Analysis

The statistical data analysis will be carried out by [name]. [name] after completion of the data collection of the entire project.

Repeated measures analysis of variance (MANOVA)

2 factors:

Factor 1: Situation (simulated altitude vs. terrestrial altitude)

Factor 2: Time (baseline, after step-up task, 0, 5, 10, 15, 20, 25, 30 min post-cold water immersion of the hand)

Repeated measures analysis of variance (MANOVA)

2 factors:

Factor 1: Situation (simulated altitude vs. terrestrial altitude)

Factor 2: Time (baseline, post-cold water immersion of the hand)

The significance level is set at $P < 0.05$, and the statistical data analysis is carried out with SPSS V. 23.

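### Seventeen outcomes are all primary and tested at an unadjusted 5%, so with no true difference the chance of at least one significant primary result is about 39–58% (17 tests, assumed correlation 0.5 down to 0)

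*Combined protocol and SAP*

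**What the plan says.** Section 4.2 states two primary goals side by side: "The primary goal is to compare and evaluate the physiological effects of terrestrial altitude and simulated altitude" and "The primary goal is to compare and evaluate the psychological effects of terrestrial altitude and simulated altitude". Under the first it lists 11 measures: skin perfusion, blood, muscle and brain oxygen saturation, heart rate, blood pressure, skin temperature, lactate, creatine kinase, balance and pain. Under the second it lists six: sleep disorder, altitude sickness, dyspnea, state of mind, sleepiness and the cognitive battery. The synopsis gives the same 17. Only thermal comfort and temperature perception are secondary.

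Some listed outcomes have several parts. Section 5.1 says "The cognitive test battery consists of 8 tasks", and balance is recorded in two units.

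Section 11.1 sets out null and alternative hypotheses block by block, without direction, for example "The perfusion of the skin microcirculation changes significantly in the simulated altitude compared to the terrestrial altitude". Three blocks each cover two outcomes, as in "Blood pressure and heart rate do not change significantly at the simulated altitude compared to the terrestrial altitude". That makes 14 blocks for the 17 primary outcomes, plus one for the secondary scales.

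Section 11.4.2 specifies a two-factor repeated-measures analysis (Situation and Time), labelled MANOVA, and then: "The significance level is set at $P < 0.05$, and the statistical data analysis is carried out with SPSS V. 23". The synopsis sets the same 5% level. The sections supplied give no ranking of outcomes, omnibus gate, adjusted alpha or rule for what counts as a positive trial.

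**The concern.** A 5% threshold applied separately to many co-equal primary outcomes does not hold the trial's error rate at 5%. If any one of them may be reported as a primary effect, the relevant figure is the chance that at least one is significant by luck. With no outcome named in advance as decisive, a reader of the results could not tell one or two chance findings from a real difference between terrestrial and simulated altitude. The sample-size calculation in 11.2 also uses alpha 0.05 for a single test, so it leaves no room for a correction.

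**Working it through.** **The plan's own figure.** The plan states no familywise error rate. Its only related figure is the 23 participants in 11.2, from f(V) = 0.9, alpha 0.05, power 0.6, 3 groups and 14 measurements. With the Pillai F approximation:

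- df1 = (3 − 1)(14 − 1) = 26 and s = 2.
- N = 23: df2 = 2 × (23 − 3 − 13 + 2) = 18, noncentrality = 23 × 2 × 0.81 = 37.26, power 0.647.
- N = 22: power 0.586.

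So 23 is reproduced, as one test at 5%. On the same inputs, N = 24 has 70% power at 0.05 but about 22% at 0.05/17 = 0.0029. Dividing alpha among 17 co-primaries is therefore not a workable repair.

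**Counts.** Outcomes: 11 + 6 = 17. Hypothesis blocks: 17 − 3 = 14, because muscle/brain saturation, blood pressure/heart rate and lactate/creatine kinase are paired.

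**Familywise error, independent tests:** 1 − 0.95^K.

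- K = 14: 51.2%
- K = 17: 58.2%
- K = 24 (the 8 cognitive tasks counted singly: 17 − 1 + 8): 70.8%
- K = 34 (Situation and Situation × Time for each outcome: 2 × 17): 82.5%

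**Familywise error, correlated tests.** The documents give no correlation, so it is varied as an assumption. The method is simulation of K equicorrelated two-sided z statistics, 200,000 replicates.

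| Correlation | 14 blocks | 17 outcomes | 24 tests | 34 tests |
|---|---|---|---|---|
| 0 | 51.2% | 58.1% | 70.8% | 82.5% |
| 0.3 | 43.9% | 49.2% | 59.5% | 69.9% |
| 0.5 | 34.7% | 38.8% | 45.8% | 53.5% |
| 0.7 | 25.0% | 27.1% | 31.3% | 35.3% |
| 0.9 | 14.2% | 14.9% | 16.3% | 17.5% |

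The expected number of false positives is 17 × 0.05 = 0.85, whatever the correlation.

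**Does the MANOVA label protect?** Nine physiological outcomes are measured at nine times. A joint Situation × Time test then needs 9 × (9 − 1) = 72 dimensions, which 24 people cannot support. A joint Situation-only test on time-averaged values needs 9 dimensions and can be fitted (9 and 24 − 9 = 15 degrees of freedom).

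**Price of control.** For a paired t-test with n = 24, df = 23, noncentrality dz × √24 and 80% power, the detectable dz is:

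- 0.60 at 0.05 (a single primary)
- 0.77 at 0.05/6
- 0.82 at 0.05/10
- 0.86 at 0.05/16

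At dz = 0.60, power is 80% at 0.05 and about 45% at 0.05/10.

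**The case against.** The strongest defence is that this is basic research. Section 10.3 says the study seeks fundamental knowledge, no efficacy claim hangs on one test, and 11.1 states expected directions for several outcomes (saturation, heart rate, blood pressure, lactate, altitude sickness). This has some force. A reader might infer that any pattern could be presented as the finding; those stated expectations limit that freedom, so the inference goes too far. The headline rate also supposes no true difference anywhere, which the studies cited in 11.1 make doubtful for some outcomes. Even so, the plan calls itself a randomized clinical trial, labels the outcomes primary and poses significance hypotheses. If exploration is meant, it should say so and drop the significance claims.

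A second defence is that MANOVA implies a joint, protective test. A reader might infer the opposite, that no joint test can be fitted and outcome-by-outcome testing is forced. Neither reading holds. Only the joint interaction test is ruled out. The evidence for separate testing is the block-by-block list in 11.1 and the absence of any joint hypothesis or gate in 11.4.2. Even on the generous reading, two models with two effects each give four omnibus tests: 1 − 0.95^4 = 18.5% if independent.

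Two further inferences fail. Not every outcome has its own hypothesis pair: there are 14 blocks, so the lower range must be shown as well. And 39–58% is not a figure the documents fix: it rests on the assumed correlation and on exactly one test per outcome.

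**Conclusion.** The point holds. Seventeen primary outcomes, tested through 14 hypothesis blocks at an unadjusted 5%, give a familywise error of about 39–58% (17 tests) or 35–51% (14 blocks) if no outcome truly differs. This assumes a common correlation between tests of 0.5 down to 0 and one two-sided test per outcome or block. Very strong correlation lowers the rate, but at 0.9 it is still about 15% for 17 tests, three times nominal. Counting the cognitive tasks singly, or both Situation and Situation × Time, raises it. This should be corrected, and the correction costs nothing in participants or measurements.

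**What to change.** Before any data are seen, revise 4.2, 5.1 and 11.4.2 (and the synopsis to match):

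- Name one primary outcome, one contrast and one test at two-sided 5%. State which terrestrial visit enters the contrast: 8.2.1 and 9.2.2 provide for measurement on arrival and again the next day, and 11.4.2 does not choose. Blood oxygen saturation is one candidate, because 11.1 cites prior data for it. It is not the only one: 11.1 also cites prior data for postural stability, heart rate, blood pressure and altitude sickness. The sponsor may choose another. If saturation is chosen, the plan should acknowledge that 8.2.1 gives different altitudes, 3530 m simulated and 3200 m terrestrial.
- Make the other 16 outcomes secondary, each with one defined measure and one composite cognitive score. Report Situation × Time descriptively with 95% confidence intervals.
- Choose one error-control scheme. (a) Test the secondaries only if the primary is significant, with Holm across all 16; this holds trial-wide error at 5%. (b) Use Holm within the physiological and psychological families and state that 5% holds only within each. With the primary, overall error can then reach about 1 − 0.95^3 = 14% if independent.
- Keep thermal comfort and temperature perception descriptive, or add them to the Holm family.

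The cost is wording in the plan, plus a real loss of status and power for most outcomes. The primary keeps a detectable dz of 0.60. The strictest Holm step needs about 0.86 under (a), or 0.82 and 0.77 under (b) with families of 10 and 6, which is the split if the primary is physiological. A legitimate alternative is to declare all outcomes exploratory, report estimates with confidence intervals and make no significance claims.

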11.4.3 Secondary Analysis

Nonexistent.

11.4.4 Interim analyses

The data is processed after the project ends. No additional interim analyses are planned.

11.4.5 Security analyses

No security analyses are provided.

11.4.6 Deviations

Deviations from the planned statistical analysis are recorded and justified and reported to the CEC in the annual report.

11.5 Drop-outs and missing data

If a test subject does not complete the experiment, any data that has already been collected is destroyed and is not included in the final data analysis.

SUPSI

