3.7 Risk / Benefits

Possible risks in the situation of terrestrial and simulated altitude are the appearance of headaches, impaired consciousness, disorientation and nausea. In addition, a doctor is present during the measurements. Subjects who may be at risk are recorded by the screening procedure and the health questionnaire and are not included in the study. However, the risk is to be classified as minor, as studies are already being conducted with obese patients and seniors under hypoxic conditions, which has not led to any complications. Participants do not derive direct benefits from participating in the study. More information on securing the test subjects can be found in chap. 8.1.1. Justification

SUPSI

for the choice of population

This series of studies is being conducted with healthy adults to minimize the health risk. The psychophysiological reactions of the body to terrestrial and simulated altitude training are assumed to be probable in this test subject population.

The test subjects are comprehensively informed about the course of the study and possible risks before they are accepted to participate in the study. You will also receive the information in written form and have the opportunity to ask questions if anything is unclear. The declaration of consent explains to them what their rights and obligations are when participating. In addition, they are informed that they may withdraw from participation at any time without giving reasons, without incurring any disadvantages as a result.

SUPSI

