7.4 Discontinuation of study participation

If a participant withdraws from the study, the lot of the allocation is returned to the pot in a new envelope and a new participant is sought.

All data collected to date will be evaluated as far as possible and included in the data analysis (in accordance with Art. 9 ClinO). After evaluation, the data is irreversibly anonymized.

The conditions for the termination of the experiment were described in chap. 5.4.

There is no disadvantage for the participants if they discontinue their participation in the study.

SUPSI

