10.3.1 Definition and recording of safety-relevant events

An adverse event (ADVERSE EVENT) AE) is any unfortunate medical occurrence in a study subject who is exposed to a simulated or terrestrial altitude (as listed in Chapter 8.1.1) that is not necessarily causally related to the study process. An AE can therefore be any adverse and unintentional sign or symptom that can be related to the intervention product (according to Chapter 8.1.1).

According to swissethics.ch, a serious adverse event (SAE) is classified as any unfortunate medical occurrence that results in death, is life-threatening, requires or prolongs hospitalization of the subject, results in a persistent or significant disability/inability, or is a congenital anomaly/birth defect. In our

SUPSI

study, an SAE is not to be expected due to the amount that is being investigated.

The equipment used in this study is used in accordance with the operating manual.

If the examination leads to a reaction described above, this is classified as a safety-relevant event by the study leader. For the affected study participant, the study is completed at this time, and the data already collected will be processed as described in chapters 7.4 and 9.1.6.

The subject-specific demographic data collection sheet (page 4) records:

- Date and time of the incident
- Course of the incident
- Persons involved & witnesses
- Study ID (specified by the CEC)
- Personal data of the person concerned (if not previously recorded)

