11.2 Sample size

The sample size in the literature varies. The planned number of 24 subjects is within the wide range and is expedient, time-wise and financially feasible for the study.

The G*Power analysis (V.3.1.) revealed (F-test, MANOVA:repeated measures, within-between interaction, effect size $f(V) = 0.9$, alpha err prob = 0.05, Power (1-beta err prob) = 0.6, number of groups = 3, number of measurements = 14) a required group of 23 participants.

11.3 Criteria for the statistical use of data in the case of incomplete data sets

Only data from subjects who have completed the entire protocol will be included in the study. This ensures that all data has been collected under the same conditions and thus remains homogeneous and comparable.

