11.4 Scheduled analyses

11.4.1 Datasets and Data Population

Only datasets that can be used sensibly will be included in the study. Incomplete data sets that contain only part of the protocol are included in the analysis as far as possible. No new test subject is being sought to replace the missing data.

SUPSI

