12.1.3 Archiving of data

The data collected will be kept for 10 years. Data protection will continue to be guaranteed.

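### The plan gives incompatible rules for participants who do not finish, and following sections 11.3 and 11.5 would probably bias the altitude-sickness comparison towards no difference

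*Combined protocol and SAP*

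**What the plan says.** Two sections of the protocol exclude participants who do not finish.

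- Section 11.3: "Only data from subjects who have completed the entire protocol will be included in the study".
- Section 11.5, on a participant who does not complete: "any data that has already been collected is destroyed and is not included in the final data analysis".

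Four sections include them. Sections 7.4 (discontinuation), 8.5 (eliminated participants) and 9.1.6 (early termination) each say that data already collected go into the analysis where feasible. Section 11.4.1 says the same of partial data sets: "Incomplete data sets that contain only part of the protocol are included in the analysis as far as possible".

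On retention, 8.5 stores the data of eliminated participants, and 12.1.3 says "The data collected will be kept for 10 years".

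On replacement, 7.4 says that after a withdrawal "the lot of the allocation is returned to the pot in a new envelope and a new participant is sought". Section 11.4.1 says "No new test subject is being sought to replace the missing data".

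Section 10.3.1 covers participants in whom the examination leads to a reaction of the kind it defines: "For the affected study participant, the study is completed at this time". The same sentence refers the handling of their data to 7.4 and 9.1.6. Section 3.7 names the expected problems: "Possible risks in the situation of terrestrial and simulated altitude are the appearance of headaches, impaired consciousness, disorientation and nausea". The altitude-sickness, dyspnoea and cognition measures are all listed as primary in 4.2.

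**The concern.** The analysis population is undefined. Sections 11.3, 11.4.1 and 11.5 disagree within the statistics chapter itself, so the choice between completers and all available data could be made after the results are seen.

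The choice matters because stopping can be caused by what is being measured. Headache and nausea are named risks of the exposure, and the trial also measures altitude-sickness symptoms as a primary outcome. The explanations in 11.1 expect more altitude sickness at terrestrial than at simulated altitude, so loss through symptoms would probably be unequal between the two situations. Under 11.3 and 11.5 the most affected people would be removed mainly because of the situation expected to be worse, which pulls the contrast towards no difference. Section 11.4.5 plans no safety analysis, so no other planned analysis would count them. Destroyed data cannot be used in a sensitivity analysis.

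**Working it through.** **1. The rules side by side**

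| Question | Exclude / no | Include / yes |
|---|---|---|
| Are partial data analysed? | 11.3, 11.5 | 7.4, 8.5, 9.1.6, 11.4.1 |
| Are partial data kept? | 11.5 (destroyed) | 8.5, 12.1.3 (10 years) |
| Participant stopped after a reaction? | 11.3, 11.5 | 10.3.1, through 7.4 and 9.1.6 |
| Is a leaver replaced? | 11.4.1 | 7.4 |

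No section sets an order of precedence.

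**2. The plan's own sample size and its margin**

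Inputs from 11.2: f(V) = 0.9, alpha 0.05, power 0.6, 3 groups, 14 measurements, required N = 23.

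- Pillai trace with p = 14 − 1 = 13, q = 3 − 1 = 2, s = 2.
- df1 = 13 × 2 = 26; df2 = s(N − 3 − 13 + s); noncentrality N × s × f(V)².
- N = 23: df2 = 18, noncentrality 23 × 2 × 0.81 = 37.26, power 0.647.
- N = 22: power 0.586.

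The smallest N reaching 0.6 is therefore 23, as stated. With 24 enrolled and no stated drop-out allowance, power is 0.70 with 24 completers and 0.59 with 22, so two exclusions take it below the planned 0.60. Under assumed drop-out of 5%, 10% and 20%, the binomial chance that at least 23 of 24 finish is 0.66, 0.29 and 0.03. This calculation assumes 3 groups and 14 measurements, whereas 11.4.2 plans 2 situations and 9 or 2 time points. It shows sensitivity to loss and nothing more.

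**3. Effect of deletion on the share with a reaction (assumed rates)**

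Let p be the true share with a reaction and d the share of those whose participation ends. Among completers the observed share is p(1 − d) / (1 − pd).

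- d = 0.5, p = 0.30: 0.15 / 0.85 = 17.6%.
- d = 0.5, p = 0.10, 0.20 and 0.50: 5.3%, 11.1% and 33.3%.
- d = 1: 0% whatever p is (worst case).

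**4. Effect on a mean difference (assumed scores)**

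Take normal scores with mean 2 and SD 1.5 at terrestrial altitude, mean 1 and SD 1 at simulated altitude, and correlation r of 0.3 or 0.6. The true difference is 1.0. If everyone above a terrestrial threshold is deleted, the completer difference is 1 − (1.5 − r) × φ(z)/Φ(z), with z = (threshold − 2)/1.5.

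- Threshold 4 (9% deleted): φ/Φ = 0.180. Result 1 − 1.2 × 0.180 = 0.78, or 1 − 0.9 × 0.180 = 0.84.
- Threshold 3 (25% deleted): φ/Φ = 0.427. Result 1 − 1.2 × 0.427 = 0.49, or 1 − 0.9 × 0.427 = 0.62.

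**5. Loss from the analysis method itself**

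Even under the inclusion rules, the repeated-measures MANOVA in 11.4.2 needs a complete set of values per participant. Someone stopped mid-visit has no post-immersion value for that visit and drops out. With an assumed 1% of cells missing independently:

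- physiological outcomes, 2 situations × 9 times = 18 cells: 0.99^18 = 0.83, about 20 of 24 complete;
- questionnaire outcomes, 2 × 2 = 4 cells: 0.99^4 = 0.96, about 23 of 24 complete.

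**The case against.** A reader might infer that the plan instructs the team to remove everyone made ill by altitude. It does not. Section 10.3.1, the rule written for these participants, points to 7.4 and 9.1.6, which include their data. They are lost only if 11.3 and 11.5 are taken to govern. That objection stands against the stronger reading. It also shows the conflict more sharply, because the specific rule says include while the statistics chapter says exclude and destroy.

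A reader might also infer that any adverse event ends participation. The trigger is narrower: a reaction to which the examination leads, classified by the study leader. The adverse-event definition in the same section also covers events without a causal link. The text does not say whether mild, expected symptoms count, and the design plainly means to record symptoms in people who continue. Section 5.3 nevertheless lets anyone who feels unwell stop, so symptom-related loss does not depend on the literal reading.

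The assumed rates may be too high. Section 8.6 admits only people who have been at this altitude before without signs of altitude sickness, and section 7.1 excludes sensitivity to altitude. This may reduce the size of the bias. It does not remove the contradiction.

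Section 11.3 defends completers-only analysis as keeping conditions homogeneous. That is a fair aim for measurement conditions, but it does not protect the comparison when finishing depends on the outcome.

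The replacement rules could be read as covering different cases, withdrawals in 7.4 and incomplete data sets in 11.4.1. A withdrawal after the first measurement produces an incomplete data set, so the two rules meet in the commonest case.

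**Conclusion.** The contradiction is on the face of the text and must be resolved before the first drop-out, since destruction cannot be undone. The documents do not establish how large the bias would be, because they give no reaction or stopping rates. If 11.3 and 11.5 were followed, the altitude-sickness contrast would probably move towards no difference. This rests on the protocol's own expectation of more sickness at terrestrial altitude and on stopping being related to symptoms. Under the assumed rates the effect is attenuation: 30% read as 17.6%, or a difference of 1.0 read as about 0.8 when the most symptomatic 9% are lost. Complete erasure occurs only in the worst case, where every reaction ends participation. No bias has been calculated for oxygen saturation or cognition, and none is claimed.

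**What to change.** - Delete the completers-only rule in 11.3 and the sentence in 11.5 that destroys and excludes data.
- State one rule, consistent with 7.4, 8.5, 9.1.6, 10.3.1 and 11.4.1: all measurements taken up to stopping are kept and analysed, whether or not the participant is replaced.
- Replace the repeated-measures MANOVA in 11.4.2 with a linear mixed model with a random participant effect on all available data. Report completers as a sensitivity analysis.
- The mixed model uses partial data but does not remove bias when stopping depends on symptoms that were never scored. Therefore also report the number stopped for symptoms by situation, with a sensitivity analysis that gives them an unfavourable altitude-sickness score fixed in advance.
- Use one replacement rule in 7.4 and 11.4.1.
- The sponsor must reconcile 10.3.1, under which a reaction ends participation, with the planned measurement of altitude symptoms. No stopping rule is proposed here.

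The cost is changed wording and slightly more analysis work. The mixed model can be fitted in SPSS, the planned software, and no extra participants or procedures are needed beyond whatever the chosen replacement rule implies.
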